### 11.4 SAFETY ANALYSIS

Adverse events occurring between enrollment and 6 weeks after surgery will be tabulated by type and grade. Adverse events that are at least possibly related to nivolumab will be tabulated separately.

Safety monitoring will occur continuously during the study. We anticipate nivolumab to be well-tolerated in this patient population and would anticipate a low ( $\leq 5\%$ ) rate of grade 3 and 4 adverse events that are at least possibly related to nivolumab. If there were strong evidence during the course of the trial that the rate of grade 3 and 4 adverse events was 25% or higher, we would stop the study. Using a likelihood-based approach, the study will stop if the likelihood ratio for a grade 3-4 AE rate of 25% vs. a grade 3-4 AE rate of 5% is 4 or higher. This is based on the binomial distribution. The stopping boundaries based on this approach are shown in the table below. Note that the upper limit on the sample size 19 due to the potential need to enroll up to 19 patients in the case of up to two patients inevaluable for response.

Stop the trial if:	Observed rate	Likelihood Ratio
2 of 3-9 pts have grade 3-4 AEs	22% - 67%	$\geq 4.78$
3 of 10-17 pts have grade 3-4 AEs	18% - 30%	$\geq 4.57$
4 of 18-19 pts have grade 3-4 AEs	21% - 22%	$\geq 4.36$

Additionally, if there is evidence that there is a delay in time to surgery due to adverse events, the study will be stopped. It would be considered acceptable if 5% or fewer of patients experienced a delay (i.e. greater than 3 weeks from their last dose of nivolumab.. A rate of delay of 10% or greater would be considered unacceptable. Given these assumptions and the use of a likelihood-based approaches as above (with a likelihood ratio of 4 or greater in favor of 20% causing study stoppage). The stopping boundaries are listed below:

Stop the trial if:	Observed rate	Likelihood Ratio
3 of 3-15 pts have a surgery delay	20% - 100%	$\geq 4.20$
4 of 9-19 pts have a surgery delay	21% - 25%	$\geq 7.11$

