### 11.3 DETERMINATION OF SAMPLE SIZE

This study will enroll up to 19 patients. The Simon two-stage design is based on a total of 17 patients who are evaluable for efficacy. We may enroll up to 19 to allow for up to two patients to be inevaluable.

Without treatment, the rate of response would be expected to be very low (<2%). With treatment, we anticipate a meaningful pathological response rate of 25%. Using a Simon optimal two-stage design with alpha of 4% and power of 91%, we can detect this difference with a sample size of no more than 17 patients. In stage 1, 9 patients will be enrolled. If none respond, the study will be stopped. If one or more responds, we will continue to the 2nd stage and an additional 8 patients will be enrolled. If a total of 2 or more patients respond out of 17 we will reject the null hypothesis and conclude that treatment with Nivolumab results in a meaningful pathological response for patients with HNSCC.

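### The surgery-delay stopping rule names two unacceptable rates, 10% and 20%; its table fits only 10%, and the table's second row contradicts its own rate column

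*Combined protocol and SAP*

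**What the plan says.** Section 11.4 (Safety Analysis) contains two whole-study stopping rules. The first concerns grade 3-4 adverse events. It names both rates (25% against 5%), sets a likelihood-ratio threshold of 4, and gives the model: "This is based on the binomial distribution".

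The second concerns delay to surgery caused by adverse events, with delay defined as more than 3 weeks from the last nivolumab dose. Its elements are:

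- Acceptable rate: "It would be considered acceptable if 5% or fewer of patients experienced a delay".
- Unacceptable rate: "A rate of delay of 10% or greater would be considered unacceptable".
- Stopping criterion, in the next sentence, which refers back to the likelihood approach of the adverse-event rule: "with a likelihood ratio of 4 or greater in favor of 20% causing study stoppage". No comparator is named.
- Table row 1: "3 of 3-15 pts have a surgery delay", observed rate 20%-100%, likelihood ratio at least 4.20.
- Table row 2: "4 of 9-19 pts have a surgery delay", observed rate 21%-25%, likelihood ratio at least 7.11.

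The upper limit of 19 comes from Section 11.3: "This study will enroll up to 19 patients".

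**The concern.** Consecutive sentences give different alternatives for one rule. A likelihood-ratio boundary is fixed by its two rates and its threshold, so 10% and 20% cannot both lie behind one table. If the 20% clause governs, the table lets the trial continue at counts where it should stop. If the table governs, the criterion in the text is wrong. No other section says which applies.

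Row 2 has its own fault. Four delays in nine patients is 44%, not a rate between 21% and 25%. The row also overlaps row 1 at 9-15 patients, so two thresholds, 3 and 4, are printed for the same sample sizes.

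The rule can end the whole study and safety is monitored continuously, so the monitoring committee needs a single threshold at every sample size.

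**Working it through.** **Formula.** For x delays in n patients, LR = (p1/p0)^x × ((1−p1)/(1−p0))^(n−x). The trial stops when LR ≥ 4.

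**Check of the formula on the adverse-event table (25% against 5%).** 2 of 9 gives 4.78 and 3 of 17 gives 4.57, both as printed.

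**Reproducing the delay table with 10% against 5%.**

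- 3 of 15: 2³ × (0.90/0.95)¹² = 4.18 (printed 4.20; the gap is of rounding size and does not move the boundary)
- 3 of 16: 2³ × (0.90/0.95)¹³ = 3.96, below 4
- 4 of 19: 2⁴ × (0.90/0.95)¹⁵ = 7.11 (printed 7.11)

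The boundaries from three patients on are therefore 3 of 3-15 and 4 of 16-19.

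**The same points with 20% against 5%.**

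- 3 of 15: 4³ × (0.80/0.95)¹² = 8.14
- 4 of 19: 4⁴ × (0.80/0.95)¹⁵ = 19.44
- 2 of 10: 4² × (0.80/0.95)⁸ = 4.05; 2 of 11: 3.41
- 3 of 19: 4³ × (0.80/0.95)¹⁶ = 4.09

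The boundaries from two patients on are 2 of 2-10 and 3 of 11-19. A threshold of four is never needed.

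**Other pairs.** The 20% clause names no comparator, so 20% against 10% was also tried. It gives 1.95 at 3 of 15 and 2.73 at 4 of 19, with boundaries from three patients on of 3 of 3-8, 4 of 9-15 and 5 of 16-19. Alternatives of 15% and 25% against 5% give 7.11 and 15.27, and 7.33 and 18.03. None matches the printed pair of 4.20 and 7.11.

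**Where the rules disagree (20% against 5% compared with the table, from three patients).**

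| Delays | Patients | LR, 20% against 5% | LR, 10% against 5% | 20% rule | Table |
|---|---|---|---|---|---|
| 2 | 3-10 | 13.47 down to 4.05 | 3.79 down to 2.60 | stop | continue |
| 3 | 16-19 | 6.85 down to 4.09 | 3.96 down to 3.37 | stop | continue |

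**Row 2.** 4/9 = 44%, 4/16 = 25%, 4/19 = 21%. The printed 21%-25% fits 16-19, which is also where the 10% against 5% boundary moves to 4.

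**Operating characteristics.** Let q_n(x) be the probability of having x delays after n patients without having stopped. Then q_n(x) = (1−p)·q_{n−1}(x) + p·q_{n−1}(x−1), keeping only x below the boundary at n. The stopping probability is 1 − Σ q_19(x).

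| True delay rate | Table (3 of 3-15, 4 of 16-19) | 20% against 5% | Difference (points) |
|---|---|---|---|
| 5% | 3.8% | 11.4% | 7.5 |
| 10% | 19.9% | 37.0% | 17.0 |
| 20% | 64.7% | 80.4% | 15.6 |

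Differences are taken before rounding. Starting the 20% rule at two or at three patients gives the same rounded probabilities. At a true rate of 20%, the expected number of patients is 13.6 under the table and 10.4 under the 20% rule started at two patients.

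**The case against.** The strongest reply is that the table plainly governs. The only rates stated as assumptions are 5% and 10%, the text presents the table as the boundaries, and both printed ratios fit 10% against 5%. The 20% appears once, in a parenthesis without a comparator, and may be a slip. That is a fair reading of how the table was built. It does not remove the fault, because the 20% stands in the clause that defines when the study stops, and a committee should not have to guess that it is a mistake. Even on this reading, the clause and row 2 need correcting.

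Taking 5% as the comparator for 20% is an inference. It is supported by the stated acceptable rate and by the reference back to the adverse-event rule. With 10% as comparator the 20% clause would be more lenient than the table, but it would still not reproduce it.

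The row 2 error is mostly editorial: up to 15 patients, row 1 already stops the trial at three delays. The harm arises only if someone lets row 2 replace row 1 from nine patients on.

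The adverse-event rule also narrows the practical gap. If every delay came from a grade 3-4 event counted under that rule, its printed table would already stop the trial at 2 of 3-9 and 3 of 10-17, leaving disagreement only at 2 of 10 and 3 of 18-19. The full gap applies when delays come from events that do not count there.

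**Conclusion.** The concern holds. The text gives two alternatives for one stopping rule, the table can be reproduced only with 10% against 5%, and row 2's patient range conflicts with its rate column. Choosing 20% instead of 10%, with 5% as comparator, raises the chance of stopping at the acceptable rate about threefold (3.8% to 11.4%) and adds 17.0 and 15.6 points at true rates of 10% and 20%.

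These figures describe the delay rule alone. They assume independent patients, a check after each one with delay status known before the next is counted, and follow-through to 19 patients. The Simon futility stop after nine patients and the adverse-event rule would reduce the trial-level difference. With overlapping accrual, the expected numbers are patients evaluated, and enrollment at the time of stopping could be higher. The primary analysis and sample size are unaffected. Correction is still needed, because a rule that ends the study must have one reading.

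**What to change.** The sponsor should decide which unacceptable rate is meant, state that rate and its comparator in both sentences, and regenerate the table from that pair. Which rate is right is not for this review to say. For reference:

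- 10% against 5% gives 3 of 3-15 and 4 of 16-19.
- 20% against 5% gives 2 of 2-10 and 3 of 11-19.

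Whichever pair is kept, the ranges should not overlap and the observed-rate column should match them.

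Two additions are worth making in the same edit. First, state the number of patients at which the rule starts. The present table implies three, but the ratio is exactly 4 at 2 of 2 (10% against 5%) and at 1 of 1 (20% against 5%); counting 1 of 1 would raise stopping at a true 5% rate from 11.4% to 14.3%. Second, report the stopping probabilities at the acceptable and unacceptable rates.

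The cost is a wording and table correction in Section 11.4, with no new data or patients.

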## **11.5 INTERIM ANALYSIS**

There are no interim analyses planned for this study. However, given that the study design is a Simon two-stage design, the number of responses in the first nine patients will be evaluated and the study will be terminated after the ninth patient if none of these nine patients have achieved a clinical response.

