## **10 DEFINITION OF ENDPOINTS**

### **10.1 PRIMARY EFFICACY ENDPOINT**

The primary efficacy endpoint is objective response rate: pathologic complete response + pathologic partial response. Objective response rate: the sum of patients with either a pCR defined as no invasive and no in situ residuals present in the surgical specimen or partial pathologic response defined at least a 30% reduction in the size of the lesion in the surgical specimen. The reduction in size will be determined by comparing the pretreatment clinical measurements (the sum of the greatest axial measurement obtained radiographically, or using calipers if necessary, at the time of initial evaluation) with the final pathologic measurements. Partial response has been chosen as an efficacy endpoint because of the two stage design and small sample size of the proposed trial (*i.e.* a objective response must be observed in at least 1 patient in first nine to proceed with the second stage). The proposed study is based on the current available head and neck squamous cell carcinoma data and is not powered to assess an objective response rate defined as pathologic complete response + major pathologic response.

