## 11.2 DATA ANALYSIS PLANS

### 11.2.1 PRIMARY OBJECTIVE

The clinical, radiographic and pathologic response rates will each be estimated with a 95% confidence interval, accounting for the two-stage design [41]. The null hypothesis is a 2% pathological response rate and the alternative is a 25% pathological response rate. If no patients respond in the first nine evaluable patients enrolled, the study will be terminated and we will conclude that there is not sufficient activity to reject the null hypothesis. The trial may pause enrollment after the first nine patients (if needed) to follow the ninth patient for a pathologic response. Note, however, that it is possible that an earlier patient may respond which would negate the need to stop enrollment (e.g. the 2nd patient may respond which would satisfy the criteria of at least one patient response in the first nine patients). If at least one patient has a pathologic response among the first nine evaluable patients enrolled, an additional eight patients will be enrolled. If two or more patients among 17 evaluable patients respond, we will reject the null hypothesis. The reported p-value will be based on two-stage design and any deviations from the intended sample size will be accounted for using the approach by Koyama and Chen [41]. Deviations from the planned sample size would only include the need for replacement patients in the event of a patient withdrawal following a single dose of Nivolumab secondary to toxicity or patient preference. If this were to occur these withdrawn patients would be excluded from the efficacy analysis. Only patients that receive at least 2 doses of Nivolumab will be included in the efficacy analysis. Briefly, Koyama and Chen's approach adjusts the final results of the Simon two-stage design (point estimate, 95% confidence interval, and p-value) by considering the evaluation of the data at the end of the 1st stage of the design. Ignoring the two-stage nature of the design, the estimated response rate (i.e. number of responders divided by the total number of patients at the end of stage 2) tends to underestimate the true response rate. In addition, the p-value and 95% confidence interval based simply on the maximum likelihood estimate using the total number of responses and total sample size will not be valid if the futility stopping evaluation is ignored. The approach for implementing the adjustment can be found here:

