### 11.2.2 SECONDARY OBJECTIVES

Immune activation markers will be graphically displayed at baseline (pre-treatment) and at time of surgical resection, and summary statistics will be reported for baseline, follow-up and changes over time. Based on our prior studies a 50% increase in immune stimulatory cytokines and 50% decrease in Treg levels is anticipated.

Transformations will be taken as needed (e.g. log transform) to adhere to assumption of statistical methods. Comparisons of baseline vs. follow-up measures will be made using paired t-tests. Logistic regression will be used to evaluate the association between baseline immune markers and clinical response and to evaluate associations between changes in immune markers and response. Both absolute change and percentage change in markers will be considered

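### Section 11.5 states the stage-1 stopping rule on clinical response, while the design in 10.1, 11.2.1 and 11.3 rests on pathologic response; the two rules can give opposite actions

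*Combined protocol and SAP*

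**What the plan says.** - **Section 11.5 (Interim Analysis)** says no interim analysis is planned, then recalls the Simon gate: "the study will be terminated after the ninth patient if none of these nine patients have achieved a clinical response".
- **Section 11.2.1 (Primary Objective)** gives the hypotheses: "The null hypothesis is a 2% pathological response rate and the alternative is a 25% pathological response rate". Its gate reads: "If at least one patient has a pathologic response among the first nine evaluable patients enrolled, an additional eight patients will be enrolled". It also lets enrollment pause after nine patients "to follow the ninth patient for a pathologic response".
- **Section 10.1 (Primary Efficacy Endpoint)** defines objective response as pathologic complete plus pathologic partial response, and says that "a objective response must be observed in at least 1 patient in first nine to proceed with the second stage".
- **Section 11.3 (Determination of Sample Size)** words its gate only in terms of patients responding, but its 25% target and its conclusion concern pathological response. It states alpha 4% and power 91%.
- **Section 11.2.1** also treats three responses as distinct: "The clinical, radiographic and pathologic response rates will each be estimated with a 95% confidence interval, accounting for the two-stage design".
- **Section 11.2.2 (Secondary Objectives)** plans logistic regression to "evaluate the association between baseline immune markers and clinical response". Section 10 does not define that term.

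**The concern.** The two gates name different outcomes, observed at different times. Section 5.2 places the clinical and radiographic assessment at days 28-35 (days 29-36 in 8.4 and 8.5), before surgery. Pathologic response is read from the surgical specimen, after resection at days 36-42 or 50-56. Section 11.5 also drops the word evaluable, so even its set of nine patients can differ from that in 11.2.1.

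Two things are at stake. First, the power and alpha in 11.3, and the Koyama-Chen p-value, estimate and interval promised in 11.2.1, all assume that the stage-1 gate is pathologic. If the trial stopped or continued on clinical response, they would not describe the trial that was run. Second, 11.5 is the section headed Interim Analysis, where a monitor or the data safety monitoring committee would naturally look for the stopping rule.

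A related minor point is that 11.2.1 applies the two-stage correction to all three response rates, although only pathologic response drives the stage-1 decision there.

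**Working it through.** **Inputs from the documents.** Stage 1 has n = 9 and stops on 0 responses. Stage 2 adds 8 patients. The null is rejected with 2 or more responses in 17. Response rates are p = 2% (null) and 25% (alternative). Sources: 11.2.1 and 11.3.

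**The plan's own figures first.** Let X1 ~ Bin(9, p) and X2 ~ Bin(8, p) be pathologic responses by stage. With the pathologic gate,

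P(reject) = P(Bin(17, p) ≥ 2) − P(X1 = 0) × P(X2 ≥ 2).

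- p = 2%: 0.0446 − 0.8337 × 0.0103 = 0.0360, which rounds to the stated 4%.
- p = 25%: 0.9499 − 0.0751 × 0.6329 = 0.9024, so 90%, against the stated 91%.
- P(stop at stage 1) is 0.834 at 2% and 0.075 at 25%.

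**Stage-1 actions side by side.**

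| Result in nine evaluable patients | 11.2.1 | 11.5 |
|---|---|---|
| No clinical, at least one pathologic | continue | stop |
| At least one clinical, no pathologic | stop | continue |

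The conflict follows from the wording alone. Its probability needs two quantities that the documents do not give, so these are assumptions:

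- s = chance that a pathologic responder shows a clinical response;
- f = the same chance for a pathologic non-responder.

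**Power under the 11.5 gate, with the final test still pathologic.**

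P(reject) = Σ over x1 of P(X1 = x1) × [1 − (1−s)^x1 × (1−f)^(9−x1)] × P(X2 ≥ 2 − x1).

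At p = 25%:

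| s | f = 0 | f = 5% | f = 10% |
|---|---|---|---|
| 1.0 | 90.2% | 92.0% | 93.2% |
| 0.8 | 84.8% | 88.3% | 90.7% |
| 0.6 | 75.5% | 81.9% | 86.4% |
| 0.5 | 68.8% | 77.2% | 83.1% |

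Power equals the design value of 90.2% at f of about 8.8% if s = 0.8, and about 16.8% if s = 0.6. At p = 2%, alpha over the same grid lies between 2.1% and 4.1%.

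**Chance that 11.5 stops despite at least one pathologic response in nine.** With c = p·s + (1−p)·f, this is (1−c)^9 − [(1−p)(1−f)]^9. At p = 25%:

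- s = 0.8, f = 0: 0.8^9 − 0.75^9 = 0.1342 − 0.0751 = 5.9%
- s = 0.8, f = 5%: 4.0%
- s = 0.6, f = 5%: 0.8125^9 − 0.7125^9 = 0.1543 − 0.0473 = 10.7%
- s = 0.5, f = 0: 22.6%

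**Chance that 11.5 continues despite no pathologic response in nine.** This is (1−p)^9 × [1 − (1−f)^9]. With f = 5%, it is 2.8% at p = 25% and 0.8337 × 0.3698 = 30.8% at p = 2%.

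**The minor point on intervals.** Two-stage 95% limits under the pathologic gate solve P(continue and X1+X2 ≥ x) = 0.025 and P(continue and X1+X2 ≥ x+1) = 0.975.

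| Responses | Two-stage | Exact binomial |
|---|---|---|
| 2/17 | 1.6% to 38.5% | 1.5% to 36.4% |
| 3/17 | 3.9% to 44.0% | 3.8% to 43.4% |

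This comparison shows how little the correction changes an interval. It does not measure the effect of a clinical gate.

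**The case against.** The strongest reply is that 11.5 is a summary, not a competing rule. It denies any interim analysis and then recalls the gate as a consequence of the Simon design, which is specified on pathologic response elsewhere. Section 11.2.1 even provides a pause to obtain the ninth patient's pathologic result. The documents also use the term clinical response loosely: 3.2 supports the prognostic value of clinical response by citing pathologic complete response, and 11.2.2 slides from clinical response to plain response within one sentence. A careful reader of the whole protocol would very likely apply the pathologic gate.

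Much of this stands. The wording is probably a slip. Only 11.2.1 uses the word pathologic in the gate sentence itself; 10.1 and 11.3 are pathologic by definition and by context. The values of s and f have no source in the documents, the effect on power can go either way, and the grid is illustration only. Sections 5.2, 8.4 and 8.5 do describe clinical and radiographic assessment, and 8.4 names RECIST 1.1, but none of them defines clinical response as an endpoint.

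The reply does not remove the contradiction. Because 11.2.1 estimates clinical and pathologic response separately, the terms cannot safely be read as synonyms, and nothing in the documents gives one section precedence.

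**Conclusion.** The concern holds. The current text contains two stage-1 stopping rules on different outcomes, and they agree in every case only if clinical and pathologic response always coincide (s = 1, f = 0). That conclusion needs no assumption. Its size does: for s from 0.5 to 1 and f from 0 to 10%, following 11.5 literally would move power from 90.2% to somewhere between 68.8% and 93.2%, while alpha stays at 4.1% or below. The risk is therefore a wrong stop or a wrong continuation, and a primary analysis that no longer matches its design, rather than material inflation of the type I error. It should be fixed because it is a decision rule and the correction is simple. The breadth of the two-stage correction in 11.2.1 and the one-point power label in 11.3 are minor.

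**What to change.** - **11.5:** replace clinical response with pathologic response as defined in 10.1, and refer to the first nine evaluable patients, as 11.2.1 does.
- **11.2.1:** confine the two-stage p-value, estimate and interval to pathologic response. Report the clinical and radiographic rates with exact binomial intervals, labelled descriptive and not adjusted for the pathologic gate. Their coverage is only approximate, because that gate decides whether N is 9 or 17.
- **11.2.2:** state which response the regression uses.
- **11.3 (separate, minor):** give power as 90%; alpha of 4% can stand.

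The first edit restores the sponsor's own design, and none of the edits changes visits, sample size or data collection. The cost is a short text amendment, which under Section 14 needs IRB approval before it takes effect.
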